### Preliminary Data:

The training procedures and lesson plans have been validated through use with four individuals with post-stroke aphasia (one with right-sided hemiplegia) who completed training and immediate post-treatment evaluation. Three participants worked with a family dog and the fourth participated in the program at the PSPCA. Consistent with our hypothesis, on program completion all four participants demonstrated ability to cue their dog(s) to perform a minimum of four out of five obedience skills commensurate with a handler skill level at or above a '1' on the *PPAHE*.

**Specific Aim 2: Define participant characteristics associated with recruitment, retention, compliance and program acceptability/satisfaction relevant for determining PATD candidacy.** *Hypothesis 2:* PWA will demonstrate high (above 80%) retention and compliance rates, and high program satisfaction, including increases in self-reported ratings of psychosocial well-being. To test this hypothesis, our primary outcome measure will be the *Assessment of Living with Aphasia* (Kagan et al., 2010), complemented by self-report of participants' PATD experience gathered through an ALA-modeled qualitative spoken interview and a written, aphasia-friendly, satisfaction survey.

**Rationale:** Our second hypothesis is supported by a growing literature regarding the physiological and psychosocial benefits of human-dog interaction (Friedmann & Son, 2009; Lundqvist et al., 2017; Odendaal & Meintjes, 2003) and the likely mechanisms of action for AAT, which include as Beetz (2017) described, "promoting the preconditions of learning" (p. 7) by increasing intrinsic motivation, attention, and positive mood and decreasing fear and stress (Beetz, 2017; Blakemore & Frith, 2005; Wholfarth et al., 2013). The direct and

Assessing an animal-assisted treatment program for adults with aphasia:  
the Persons with Aphasia Training Dogs (PATD) Program

regular interaction with dogs provided in the PATD program also provides for 'active engagement' with the animal, which may support greater potential for deriving these benefits than simply having the dog present (Dietz et al., 2012).

**Feasibility Metrics:** We will track *recruitment rates* appropriate to the creation of a CONSORT flow diagram (e.g., Horton et al., 2016) including: # contacted, # screened, # eligible (vs. ineligible), # consented/enrolled (vs. declined).. Similarly, participant *retention rates* will be tracked including: # completing baseline assessment, # completing immediate post-treatment assessment, and # completing follow-up assessment. Participant withdrawals will be tracked for whether initiated by researcher or participant. Participant *compliance rates* will be tracked including # assessment and training sessions (relative to total possible) completed, and # self-reported home practice sessions.

**Outcome Measurement:** The primary quantitative outcome measure of acceptability, the *ALA*, is a pictographic self-report measure of quality of life developed to assess the impact of aphasia on daily life. Questions address participants' perceptions of aphasia, their environment, their relationships, their community engagement, experiences of self-confidence and respect, and their progress toward "living well with aphasia". Participants respond by pointing to a visual analog scale, providing for quantification of responses, and rendering the tool accessible to those with language impairment. Overall score and subdomain scores have demonstrated acceptable-to-high test-retest reliability and internal consistency (Simmons-Mackie et al., 2014). To augment standardized evaluation, the PI has developed a complementary interview, consistent with the format of the *ALA*, to more specifically probe PATD participants' perceptions of the impact of the training program. Participant narratives produced during the administration will be supported using interviewing strategies appropriate for persons with aphasia (Luck & Rose, 2007). A written, visual analog scale satisfaction survey designed to adhere to guidelines of 'aphasia-friendly' written materials will also be administered. We anticipate the assessment battery will take approximately 3 hours to complete.

**Outcome Measurement/Participation Timeline:** Participants will be randomized into immediate and waitlist treatment groups using permuted block randomization with stratification. Analysis between these two arms will be exploratory only in nature, and will inform us regarding the feasibility of the waitlist control design for use in a larger clinical trial. All participants will be evaluated before training begins, immediately following training, and at a 3-month follow-up. Participants in the delayed arm will participate in two pre-training evaluations, one immediately upon enrollment and one at the end of the delay period immediately before beginning training.

Week	1	2	3	4	5	6	7	8	9	10	11	12	13	
Immediate	Pre-training eval.	Skill 1	Skill 2	Skill 3	Skill 4	Skill 5	Post-training eval.							Follow-up eval. (week 19)
Waitlist	Pre-training eval.						Pre-training eval.	Skill 1	Skill 2	Skill 3	Skill 4	Skill 5	Post Training Eval.	Follow-up eval. (week 25)

**Statistical Considerations:** Primary outcome evaluation will be done with the entire sample of twenty. The mean pre-to-post-training change in each *ALA* domain score will be computed with the corresponding 90% confidence interval. With the total sample size of 20 subjects, the width of the two-sided 90% confidence interval is equal to 0.39 standard deviations of the pre-to-post-training changes. For the secondary analysis, we will evaluate the mean difference in each *ALA* domain scores between the immediate and delayed treatment arms at week 7 using the two-sided 90% confidence interval and two-sided two-sample t-test with alpha 0.1 (reflective of the small size pilot study). The results of comparison between the immediate and delayed treatment arms will be used to inform a future larger clinical trial. Qualitative data derived from narratives produced by PWA during administration of the PATD *ALA*-supplement will be orthographically-transcribed for offline analysis consistent with procedures detailed by Luck & Rose, 2007.

**Scientific rigor:** Participants will be assessed by a certified speech-language pathologist (SLP) who is not involved in PATD training. All assessment sessions will be video-recorded. A portion (approximately 20%) of the data will be selected for evaluation of intra- and inter-rater reliability. Inter-rater reliability will be conducted

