### Recruitment

A minimum of twenty participants with chronic (> 6 months post) stroke-aphasia will be enrolled. Participants will be recruited from the MRRI Research Participant Registry and through additional venues. The MRRI Research Participant Registry is a database of individuals who have previously consented to being contacted regarding research opportunities (Schwartz et al., 2005). The database includes approximately 302 individuals with stroke-aphasia, with an average of 43 enrollees each year, who have self-selected for interest in research participation. Additional recruitment strategies will include use of IRB approved fliers, which may be posted on websites, social media (e.g., ARCH, Aphasia Recovery Connection, or Poems in Speech Facebook pages) included in newsletters (e.g., the Aphasia Resource Collaboration Hub), shared with individuals who have previously expressed interest in the PATD program, and provided to internal (Jefferson Moss-Magee Rehabilitation) and local community-based speech-language pathologists who work with people with stroke-to share with their clients. The study may also be posted on the Thomas Jefferson University Clinical Trials Finder and study staff may present information about the study at internal (Jefferson Moss-Magee Rehabilitation) and local community aphasia-groups and events. Recruitment will also occur using the Recruitment Enhancement Services provided by the Jefferson Clinical Research Institute at Thomas Jefferson University. Recruitment Enhancement Service (RES) provides assistance to the principal investigator in developing the study's recruitment plan and may assist in identifying and contacting potential participants using the Informatics group, internal communication resources, community contacts, and other available resources as outlined in the study team's protocol. MyChart may also be used to identify and generate lists of potential participants. Individuals identified by the RES as meeting eligibility criteria will be contacted by either postal mail or email.

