## Assessing an animal-assisted treatment program for adults with aphasia: the Persons with Aphasia Training Dogs (PATD) Program

Participants will be informed that they may withdraw from the study at any time, without penalty, and contact personnel are provided on the consent form. Participants will be informed that they can contact the PI at a later time if they would like to spend time reviewing the information in order to avoid them feeling pressured to participate. They will also be informed that pre- or post-consent screening or behavioral test results may indicate that they are not eligible to continue with the study. Pre-consent, research candidates from outside of the MRRI Research Registry will be screened to confirm diagnosis and related medical information and for geographic eligibility.

Assignment into each arm will be done using block randomization with stratification. Interested participants will be screened for one of two strata: 1) participation with a family dog or 2) participation through the Pennsylvania SPCA (PSPCA). Interested participants will be automatically assigned to the PSPCA condition if a) they do not have a family dog or b) their family dog is not eligible to participate. There will be no minimum requirement for assignment into either stratum.. As participants are enrolled in either the PATD or PATD-PSPCA condition, they will be block randomized into either immediate or waitlist treatment groups. Recruitment will be ongoing, until a minimum of ten PATD immediate and ten PATD waitlist participants have been enrolled.

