**Retention plan:** Strategies to encourage retention will include: 1) The timeline of the study will be detailed in recruitment and consent materials to indicate that multiple sessions are required for the study and that there will be a lag period between some phases of the study. 2) Scheduling of assessment and training sessions will be done, to the maximum extent possible, at the convenience of study participants. Assistance with travel arrangements to attend assessment sessions may be offered, Moss Rehabilitation Research Institute contracts with third-party vendors for this purpose. 3) Participants will be informed that they may continue or enroll in standard of care rehabilitation or therapy during the duration of their participation, but will be asked to inform study staff of any changes. 4) Participants will be asked to not enroll in any other research activities through completion of the immediate post training evaluations (with the speech-language pathologist and with the dog trainer). and will be asked to not enroll or participate in any other dog training activities for the duration of the study through the follow-up evaluations. 5) Participants will be informed at enrollment of the timeline for participation.

**Study Timeline:** Lesson plans consistent with the example in figure 1 have been written for all target obedience behaviors and validated with four participants with aphasia. Additional training and evaluation materials have been developed and piloted with these participants by the PI. Certified SLPs will have prior experience with PWA such that any training required on battery instruments will be minimal and will not delay data collection. CPDTs are positive reinforcement practitioners and have consulted with the PI on the lesson plans and adapted *PPAHE*. From the study start date (date of first enrolled participant) recruitment, enrollment will continue through week 72 of the study to provide sufficient time for later enrolled participants to complete either protocol. Data collection and analysis will be ongoing, with preliminary dissemination of findings anticipated to begin once enrollment has ended.

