## RESEARCH DESIGN AND METHODS

### Study Procedures and Materials

Cognitive-linguistic and psychosocial assessment sessions for all groups will take place at the Moss Rehabilitation Research Institute. Participants will complete either 3 (immediate arms) or 4 (delayed arms) assessment (dx) sessions over the course of either 19 or 25 weeks, respectively (Table 1); we anticipate that each assessment session will take approximately three hours to complete. The instruments included in these assessments will be the *Assessment of Living with Aphasia* (Simmons-Mackie et al., 2014), the PATD-program ALA supplement (developed by the PI for this study, not administered in pretraining evaluation(s)) the *Confidence after Stroke Measure* (Horne et al., 2017), and the *Behavioural Assessment of Dysexecutive Syndrome* (Wilson et al., 1996). Participants will also complete at baseline the *Western Aphasia Battery-Revised* (WAB-R, Kertesz, 2006) to provide a profile of their aphasia. The WAB-R will not be repeated.

Assessing an animal-assisted treatment program for adults with aphasia:  
the Persons with Aphasia Training Dogs (PATD) Program

All participants will be evaluated before training begins, immediately following training, and at a 3-month follow-up. Participants in the delayed arm will participate in two pre-training evaluations, one immediately upon enrollment and one at the end of the delay period immediately before beginning training.

Week	1	2	3	4	5	6	7	8	9	10	11	12	13	
Immediate	Pre-training eval.	Skill 1	Skill 2	Skill 3	Skill 4	Skill 5	Post-training eval.							Follow-up eval. (week 19)
Waitlist	Pre-training eval.						Pre-training eval.	Skill 1	Skill 2	Skill 3	Skill 4	Skill 5	Post Training eval.	Follow-up eval. (week 25)

Table 1: Sequence of participation

PATD training sessions will take place either at participants' homes, for those working with a family dog, or at the PSPCA. Training sessions that take place at the PSPCA will occur in an enclosed room, in an open indoor space in which the dog is tethered or on-leash, or in a fenced-in outdoor yard.

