### Behavioral assessments

Anticipated risks are minimal and include fatigue or frustration during the behavioral sessions. To protect against fatigue, participants will be informed they may stop or take a break at any time without penalty. Participants will be invited to take breaks as necessary and reminded that they may cease participation at any time. It is recognized that some participants may demonstrate discomfort while completing the assessments of quality of life. They are informed that some of the questions they will be asked will deal with their personal experiences and emotions related to living with aphasia, and reminded that they may choose not to answer specific questions or may forego this assessment entirely. Participants may also be offered referral information

Assessing an animal-assisted treatment program for adults with aphasia:  
the Persons with Aphasia Training Dogs (PATD) Program

for psychological care, if interested. Risks associated with travel to and from behavioral assessment sessions are anticipated to be not more than those associated with urban daily life.

Dog-training

Risks associated with interaction with dogs include the possibility of physical injury and the risks associated with coming into contact with fur, saliva, waste, or zoonotic disease associated with dogs. Before beginning work with dogs, participants will be provided with guidance on universal precautions. PSPCA participants will receive a pictographic information sheet.

Dogs are screened through either owner-report (for family dogs) or PSPCA behavior staff-report for eligibility. Participants are informed that the program is directed toward training basic obedience skills, not remediation of behavior 'problems', and that the PI conducting the training is not a certified-professional dog trainer. Dogs with a reported history of bites, reactivity (e.g., barking, growling) toward strangers, or resource guarding are excluded. It is anticipated that for participants working with a family dog, risks will not be more than those otherwise experienced in regular interaction with the dog.

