## Assessing an animal-assisted treatment program for adults with aphasia: the Persons with Aphasia Training Dogs (PATD) Program

### Data and Safety Monitoring Plan

The PI will serve as the Data and Safety Monitor. Study data are accessible to the PI at all times. The PI will maintain regular contact with the CPDTs and SLPs conducting and scoring behavioral assessments. As provided either through narrative interview or extemporaneously by participants, the PI will evaluate participant feedback related to their satisfaction with the program. Participants are free to stop their participation at any time throughout the course of the program. On an ongoing basis, safety associated with working with dogs will be evaluated by the PI, who will revise procedures as needed. Adverse events, including Serious Adverse Events and Unanticipated Problems, will be reported consistent with AEHN IRB procedures,

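### The Aim 2 primary analysis assumes twenty pre/post pairs, but the plan tolerates losses and makes no provision to collect post-training ALA, interview or survey data from people who stop training

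*Combined protocol and SAP*

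**What the plan says.** Under Specific Aim 2, Statistical Considerations, the protocol says: "Primary outcome evaluation will be done with the entire sample of twenty". The primary estimate is the mean pre-to-post change in each ALA domain with a 90% confidence interval. The stated precision, 0.39 SD of the change, is for 20 subjects and is repeated under Statistical Design and Power.

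On numbers, the Recruitment section says: "A minimum of twenty participants with chronic (> 6 months post) stroke-aphasia will be enrolled". It later adds: "Recruitment will be ongoing, until a minimum of ten PATD immediate and ten PATD waitlist participants have been enrolled". The Study Timeline says that "enrollment will continue through week 72 of the study to provide sufficient time". The trigger counts people enrolled, not people with outcome data, and no dropout allowance or replacement rule is given.

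On losses, Hypothesis 2 is that "PWA will demonstrate high (above 80%) retention and compliance rates, and high program satisfaction". Under Behavioral assessments, participants are reminded, about the quality-of-life questions, that "they may choose not to answer specific questions or may forego this assessment entirely". The Data and Safety Monitoring Plan says: "Participants are free to stop their participation at any time throughout the course of the program". The Recruitment section also warns that results obtained after consent may make someone ineligible to continue.

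On people who leave, Feasibility Metrics counts those completing each assessment point, sessions attended out of those possible, home practice, and whether the researcher or the participant initiated a withdrawal. The reason for stopping is not listed. Study Procedures and Materials says the PATD interview supplement is not given before training. The timing of the satisfaction survey is not stated. No analysis set, missing-data rule or sensitivity analysis is described.

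**The concern.** A paired change exists only for people with both scores. If twenty enrol and any of them lacks a post-training ALA, the stated analysis set does not exist and the plan names no other. The default is then whoever has both scores.

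Aim 2 asks how acceptable the programme is and who is a candidate for it. People who stop bear directly on that question. If some stop because the programme does not suit them, and nobody asks them for an ALA or a survey, the average change and the satisfaction ratings would lean towards Hypothesis 2. This has to be settled in advance, because a post-training assessment that was never offered cannot be recovered at analysis.

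**Working it through.** **Inputs.** From the document: 20 subjects, a two-sided 90% interval, stated precision 0.39 SD, retention goal above 80%, recruitment trigger of at least 10 + 10 enrolled. Assumed, because the document gives no figure: the retention rate, and the ALA change in people who are lost.

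**1. The plan's own figure.** For a paired mean, the half-width in SD units is t(0.95, n − 1)/√n. With n = 20 this is 1.729/4.472 = 0.387, which is the stated 0.39. It reproduces only as a half-width and only with 20 complete pairs. The full width is 2 × 0.387 = 0.77 SD, so the word width in both sections is a mislabel.

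**2. Losses that the retention goal allows.** 17/20 = 85% is above 80%; 16/20 = 80% is not. Up to three losses of twenty therefore count as success. The goal is not tied to a time point. If it refers to the post-training evaluation, meeting it leaves at least 17 attending; an ALA that is skipped there could lower the number of pairs further.

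**3. Precision with fewer pairs.**

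| Pairs | Half-width (SD) | Full width (SD) |
|---|---|---|
| 20 | 0.387 | 0.773 |
| 19 | 0.398 | 0.796 |
| 18 | 0.410 | 0.820 |
| 17 | 0.423 | 0.847 |
| 16 | 0.438 | 0.877 |

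At 17 pairs the interval is about 10% wider (0.423/0.387 = 1.09 to 1.10, depending on rounding).

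**4. How likely twenty pairs are.** If exactly twenty enrol and each is retained independently with probability r, the chance that all twenty are retained is r^20: 1.2% at r = 0.80, 3.9% at 0.85 and 12.2% at 0.90.

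**5. Selection.** With 17 observed (mean change m) and 3 lost (mean change c), the mean over all enrolled is (17m + 3c)/20. Take m = 0.5 SD as an illustration:

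- c = 0.5: 0.50 SD, no bias.
- c = 0: 0.425 SD.
- c = −0.25: 0.3875 SD.
- c = −0.5: 0.35 SD.

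Whenever c = 0, the observed mean is 20/17 = 1.18 times the all-enrolled mean, whatever m is. If the lost did better than those who stayed, the bias would run the other way.

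**The case against.** The strongest reply is that the quoted sentence contrasts with the secondary comparison of arms, so it may mean only that both arms are pooled. That is a fair reading, and the right to skip an assessment is a participant protection, not a flaw. But the stated precision is still tied to twenty pairs, and no rule says what happens with fewer.

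A reader might infer several stronger things that the documents do not support:

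- *Enrolment stops at twenty.* Twenty is a minimum throughout, and enrolment can run to week 72. Recruitment may close at twenty; it need not. Replacement is neither provided for nor ruled out.
- *People who stop give no data.* The plan is silent. It says all participants are evaluated before training, after training and at three months. The monitoring plan also lets the PI consider satisfaction feedback offered informally, although that is unstructured and goes to the person who delivers the training.
- *Stopping training is treated as leaving the study, and a waitlist loss before Skill 1 is treated like abandoned training.* The session and assessment counts in Feasibility Metrics can separate these cases.
- *Acceptability rests on completers only.* Retention and compliance, also part of Hypothesis 2, include people who stop. The gap is in the ALA, interview and survey.
- *A percentage satisfied would be inflated by a known amount.* The survey is a visual analog scale and the plan sets no cut-off for being satisfied, so no such percentage can be derived.

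It is also true that the direction of bias is not established: no reasons for stopping are given, and they may have nothing to do with the programme.

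**Conclusion.** The point holds in limited form. The plan rests the Aim 2 primary change and its precision on twenty pairs, while its recruitment trigger, its retention goal and the right to skip the assessment all allow fewer. It has no provision to obtain the ALA, interview or survey from people who stop training.

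The effect on precision is minor: 0.39 to 0.42 SD half-width with three losses. The effect of selection is uncertain. It is 18% of the all-enrolled mean if three are lost and their change is zero, nothing if they resemble those who stayed, and more if they worsened. These are illustrations, not estimates. For an estimation-only feasibility study this is a worthwhile, low-cost improvement and does not invalidate the design.

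**What to change.** 1. In Feasibility Metrics and the Aim 2 Statistical Considerations, state that participants who stop training without withdrawing consent are invited to the scheduled post-training evaluation (week 7 or 13). Offer them the existing aphasia-friendly satisfaction survey when they stop, and record the reason for stopping.
2. Replace the sentence on the analysis sample with: both arms pooled, all participants with a pre- and a post-training ALA. Report that number against all enrolled and against all who began Skill 1. Because this is a complete-case analysis, add a simple sensitivity analysis, for example zero change where the post score is missing.
3. In both places where precision is stated, give the 90% half-width as 0.39 SD (full width 0.77 SD) with 20 pairs, and 0.42 SD (full width 0.85 SD) with the 17 pairs that the retention goal allows.
4. Report survey ratings with the number responding out of all who began Skill 1, and report losses before Skill 1 separately. Do not count non-responders as not satisfied unless a cut-off is defined in advance.

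The cost is wording, one more occasion for an existing survey, and some assessor time. The plan puts an evaluation at about three hours, so three people who stop would need about 3 × 3 = 9 hours, with possible travel assistance. The stated precision becomes slightly less favourable, and the satisfaction results may too.

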### Statistical Design and Power

For this feasibility study, we anticipate enrolling a minimum of twenty participants with stroke-aphasia.

Scores from weekly probes will allow for analysis of change in level of 'competence' over time, as determined using the *PPAHE* for that skill. For the purpose of statistical analyses of weekly evaluations, three scores (0="not ready", 1="ok", 2="best") will be dichotomized as competent (1 or 2) vs. not competent (0). In addition to the weekly evaluations, at the end of the training period, each participant will receive a summative score on the adapted *PPAHE*. This score may range from 0 to 10. For the primary analysis, the proportion of subjects that successfully completed the training will be quantified with the corresponding two-sided 90% exact binomial confidence interval. For the secondary analysis, (i) the median cumulative score will be computed with the corresponding two-sided 90% distribution-free confidence interval (Hahn & Meeker, 2011) and (ii) the weekly competence scores will be analyzed using the repeated measures logistic regression model. With the total sample size of 20 subjects, the width of the two-sided 90% exact binomial confidence interval is at most 0.38 if the observed proportion of subjects successfully completed the training is 0.5. The interval is narrower if the observed proportion of successes is higher (or lower) than 0.5.

The mean pre-to-post-training change in each ALA domain scores will be computed with the corresponding 90% confidence interval. With the total sample size of 20 subjects, the width of the two-sided 90% confidence interval is equal to 0.39 standard deviations of the pre-to-post-training changes. For the secondary analysis, we will evaluate the mean difference in each ALA domain scores between the immediate and delayed treatment arms at week 7 using the two-sided 90% confidence interval and two-sided two-sample t-test with alpha 0.1 (reflective of the small size pilot study). The results of comparison between the immediate and delayed treatment arms will be used to inform future larger studies. Qualitative data derived from narratives produced by PWA during administration of the PATD ALA-supplement will be orthographically-transcribed for offline analysis of themes discussed consistent with procedures detailed by Luck & Rose, 2007.

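### The primary ALA result is an uncontrolled pooled pre-to-post change, and the planned randomised week-7 comparison ignores the week-1 baseline and the waitlist arm's untrained change

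*Combined protocol and SAP*

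**What the plan says.** Specific Aim 2 names the ALA as the primary measure for Hypothesis 2, which includes a predicted rise in self-rated psychosocial well-being. Under Statistical Considerations for that aim: "Primary outcome evaluation will be done with the entire sample of twenty". Statistical Design and Power gives the estimate: "The mean pre-to-post-training change in each ALA domain scores will be computed with the corresponding 90% confidence interval". The precision claimed with 20 participants is that "the width of the two-sided 90% confidence interval is equal to 0.39 standard deviations of the pre-to-post-training changes".

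The between-arm analysis is secondary: "we will evaluate the mean difference in each ALA domain scores between the immediate and delayed treatment arms at week 7". Its method is a 90% interval with a t-test at a two-sided alpha of 0.1. Outcome Measurement/Participation Timeline gives its status: "Analysis between these two arms will be exploratory only in nature". Both statistical sections say that this comparison is what will inform later, larger studies. On numbers: "Recruitment will be ongoing, until a minimum of ten PATD immediate and ten PATD waitlist participants have been enrolled".

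On visits: "Participants in the delayed arm will participate in two pre-training evaluations, one immediately upon enrollment", with the second at the end of the delay. The timeline table puts these at weeks 1 and 7 and the waitlist post-training visit at week 13. The immediate arm is evaluated at weeks 1 and 7, before and after training. Both waitlist visits carry the same pre-training label, and no section says which one starts the pre-to-post change.

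**The concern.** A single-group change contains everything that moves the score between two visits. The ALA is self-reported and repeated at each evaluation. The Retention plan lets participants continue or start usual therapy. The Outcome Measurement section cites acceptable-to-high test-retest reliability, but reliability concerns the ordering and scatter of scores and does not exclude a shift in the mean. A positive pooled change could therefore be read as confirming Hypothesis 2 when the programme did nothing.

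The design already collects what is needed to check this: a six-week untrained interval in the waitlist arm, and a week-1 score in both arms. No stated analysis estimates the untrained change, and the week-7 comparison does not use the week-1 score.

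The undefined pre-training visit adds a second problem:
- If it is week 7, the pooled change mixes first-to-second administrations (immediate arm) with second-to-third (waitlist), and the waitlist week-1 score enters no stated ALA analysis.
- If it is week 1, the waitlist change spans 12 weeks against 6 in the immediate arm.

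**Working it through.** **Inputs from the documents.** 20 participants, 10 per arm; 90% intervals; two-sided alpha 0.1; ALA at weeks 1 and 7 in both arms and at week 13 in the waitlist arm.

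**Assumed, because the documents give no figure.** Drift of 0.1 to 0.5 SD of the change score; correlation r between ALA scores at two visits of 0.5 to 0.9; equal score SD at each visit.

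**1. The plan's own precision figure.** Half-width = t(0.95, 19)/√20 = 1.729/4.472 = 0.387 SD of change. Full width = 0.773. The stated 0.39 is therefore the half-width, labelled as the width.

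**2. Pooled change under drift alone.** With true programme effect zero and drift d (in SDs of change), the t statistic is noncentral t with 19 df and noncentrality d√20. The chance that the lower 90% limit exceeds zero is P(T > 1.729):

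| Assumed drift d | d√20 | Chance interval is wholly above zero |
|---|---|---|
| 0 | 0 | 5% |
| 0.1 | 0.447 | 11% |
| 0.2 | 0.894 | 22% |
| 0.3 | 1.342 | 36% |
| 0.5 | 2.236 | 70% |

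**3. If week 1 is the waitlist pre-training visit.** With drift linear in time, average drift is (1 + 2)/2 = 1.5 times the six-week drift. A drift of 0.2 SD per six weeks becomes 0.3, and the chance rises from 22% to 36%. A drift of 0.3 becomes 0.45, and the chance rises from 36% to 62%.

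**4. The planned week-7 comparison.** Half-width = t(0.95, 18)·√(2/10) = 1.734 × 0.447 = 0.78 score SD; full width 1.55. Power is 29% for a true difference of 0.5 SD and 69% for 1.0 SD; 80% power needs about 1.16 SD.

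**5. The same comparison adjusted for the week-1 score (ANCOVA).** Full width = 2·t(0.95, 17)·√(0.2(1 − r²)), with t = 1.740. The pooled change is put on the same scale as 0.773·√(2(1 − r)).

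| r (assumed) | Raw week 7 | Week-7 ANCOVA | Pooled change |
|---|---|---|---|
| 0.5 | 1.55 | 1.35 | 0.77 |
| 0.7 | 1.55 | 1.11 | 0.60 |
| 0.9 | 1.55 | 0.68 | 0.35 |

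All widths are in score SDs. At r = 0.7 adjustment narrows the controlled interval by 1 − 1.11/1.55 = 28%. Adding the dog stratum costs one more degree of freedom (t = 1.746 instead of 1.740), under 1% of the width. The formula ignores chance baseline imbalance, which would widen the interval somewhat.

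**6. Waitlist untrained change alone.** Half-width = t(0.95, 9)/√10 = 1.833/3.162 = 0.58 SD of change. This is a coarse check on drift.

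**7. A mixed model over all evaluations with one trained yes/no term.** Take no drift and a true effect of 0.5 SD just after training that fades to zero by the 3-month follow-up. With a random intercept (intraclass correlation 0.7, 10 per arm), the expected trained coefficient is 0.77 with a linear term for administration number and 0.73 with one for weeks. That overstates the effect by about half.

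**The case against.** The strongest reply is that the plan already has a control. The week-7 comparison is randomised, both arms are then at their second ALA administration, and common drift cancels in expectation. A reader might infer that the study has no control for drift; the documents do not support that. A reader might also infer that the next trial would be planned on an inflated pooled change. Both statistical sections instead say that the between-arm comparison will inform it. Nor can one say flatly that the waitlist week-1 score is unused, because it may be the undefined pre-training value.

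It is also fair that this is a feasibility study. The Synopsis makes within-subject analysis the main approach, no efficacy decision rule is attached to the pooled interval, and the ALA is introduced as a measure of acceptability. Participants are at least six months post-onset and must be stable, so drift may be small: at 0.1 SD the false-positive chance is 11%, not 70%.

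Finally, a single model over all visits looks like an easy remedy, but step 7 shows that it can create its own inflated estimate.

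These replies narrow the point but do not remove it. Hypothesis 2 predicts an increase, and the result assigned to it cannot attribute one to the programme. The comparison that can is labelled exploratory and discards the baseline.

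**Conclusion.** The point stands in limited form. The primary ALA change is uncontrolled and cannot carry a statement about programme benefit. The planned control exists but is less precise than the collected data allow. The untrained waitlist change goes unreported, and the waitlist pre-training visit needs defining.

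The size depends on drift that the documents do not quantify: 11% to 70% of trials would show a pooled interval wholly above zero with no programme effect, for assumed drifts of 0.1 to 0.5 SD of change, against 5% with none. The precision gain from adjustment depends on the assumed correlation: width 1.35 to 0.68 score SD for r of 0.5 to 0.9, against 1.55 as planned.

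Even the adjusted comparison removes only what is common to both arms. Participants know whether they have been trained and the ALA is self-reported, so expectation remains in any estimate.

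**What to change.** In Statistical Considerations for Specific Aim 2 and in Statistical Design and Power:

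1. Keep the pooled pre-to-post change with its 90% interval as a descriptive within-person result, and state that week 7 is the pre-training value for the waitlist arm.
2. Report beside it the waitlist week 1-to-7 change with its 90% interval.
3. Replace the raw week-7 comparison with an ANCOVA of the week-7 ALA score on arm, week-1 score and dog stratum (family dog or shelter).
4. Base any statement about programme benefit on that controlled estimate.
5. If a mixed model is also fitted, leave out the 3-month follow-up or give it its own term.

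The cost is wording and one modest model, with no new visits, participants or measures. The downside is precision: at r = 0.7 the controlled interval is about 1.11 score SDs wide against 0.60 for the pooled change. That is the price of an estimate free of common drift.
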